## 2. For superiority of both the DVD-delivered and the face-to-face programme over 'usual care'

For the superiority sample size calculations, there is no widely acceptable MCID for between group change in AQLQ, although the MCID for within person change in AQLQ is reported to be 0.5 (SD 0.41) (31). Therefore, we approached the superiority sample size calculation in two ways. Firstly, using the published within person MCID of 0.5 and secondly, using estimates from the GLAD study, a between group mean (SD) difference in AQLQ at 6 months of 0.38 (1.03). Using an MID of 0.5

Nquery 7.0 (specifically the MTTOU-1 two group t-test of equal means – unequal n's program) shows that a two group t-test with a 5% one-sided significance level will have 90% power to detect a difference in mean AQLQ of 0.5 or greater, assuming that the common standard deviation is 0.41, when the

BREATHE Page 26 of 35 Protocol v6 01-08-2014

sample sizes are 10 in the face-to-face breathing retraining and 20 in the 'usual care' groups.

Similarly, a two group t-test with a 5% one-sided significance level will have 90% power to detect a difference in mean AQLQ of 0.5 or greater, assuming that the common standard deviation is 0.41, when the sample size is 13 in each of the DVD-delivered and 'usual care' groups.

Using an MID of 0.38

A two group t-test with a 5% one-sided significance level will have 92% power to detect a difference in mean AQLQ of 0.38 or greater, assuming that the common standard deviation is 1.03, when the sample sizes are 105 in the face-to-face breathing retraining and 210 in the 'usual care' groups.

Similarly, a two group t-test with a 5% one-sided significance level will have 90% power to detect a difference in mean AQLQ of 0.38 or greater, assuming that the common standard deviation is 1.03, when the sample size is 130 in each of the DVD-delivered and 'usual care' groups.

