#### 1. For equivalence of DVD programme and face-to-face programme.

In a previous HTA study comparing different pharmacotherapy options in asthma (the ELEVATE study, Controlled-Trials.com number, ISRCTN99132811, Price et al, 2011), treatments were deemed to be equivalent if the 95% CI for mean difference between groups in AQLQ was wholly included between -0.3 and +0.3. Our sample size calculation for equivalence therefore uses the same equivalence boundary (i.e. between -0.3 and +0.3). However, we have assumed that the SD of the between group difference in AQLQ will be a conservative 25% smaller (i.e. 0.77) than that reported in our GLAD study (1.03). The justification for this is that the proposed equivalence analysis will compare two breathing training interventions as opposed to a breathing intervention versus usual care in the GLAD study. Since this is an equivalence study, as opposed to a non-inferiority study, a two-tailed 5% significance level was used in the calculations (29). Following published guidelines (30), the equivalence margin was therefore selected to be 'the largest difference that can be judged to be clinically acceptable and should be smaller than differences observed in superiority trials of the active comparator'.

Using Nquery 7.0 (specifically the MTEOU-1 two group t-test of equivalence in means – unequal n's program), the following justification of the sample size is obtained:

Sample sizes of 210 in the DVD breathing retraining group and 105 in the 'face-to-face' physiotherapy group are required to assess treatment equivalence with 90% power using an equivalence boundary for AQLQ of 0.3. This assumes: that the expected between group difference in mean AQLQ is zero; a two tailed 5% significance level; common standard deviation for AQLQ of 0.77 and a lower/upper limit of -0.3/+0.3 for the 95% confidence interval of the between group difference in AQLQ.

In the unlikely event that the between group AQLQ standard deviation is higher than our estimated 0.77, assuming all other parameters stayed the same, we would still have 80% power to declare equivalence between the DVD breathing retraining group and the 'face-to-face' physiotherapy group as long as the between group SD was no higher than 0.89.

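### The first superiority calculation enters 0.41, reported only with a within-person MCID, as the between-patient SD; with the protocol's other SDs its stated 90% power is about 33–50%

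*Protocol*

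**What the plan says.** Protocol section 8.1, sample size part 2 (superiority), concedes that "there is no widely acceptable MCID for between group change in AQLQ" and adds that "the MCID for within person change in AQLQ is reported to be 0.5 (SD 0.41"). It then sizes the superiority comparisons in two ways.

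- **First way.** The target difference is 0.5, the SD is 0.41 and the test is one-sided at 5%. With 10 face-to-face and 20 usual care patients the comparison "will have 90% power to detect a difference in mean AQLQ of 0.5 or greater". For DVD against usual care the same power is claimed "assuming that the common standard deviation is 0.41, when the sample size is 13 in each of the DVD-delivered" programme and usual-care arms.
- **Second way.** The inputs come from the earlier GLAD trial: "a between group mean (SD) difference in AQLQ at 6 months of 0.38 (1.03"). The 1.03 is entered as the common SD. The protocol states 92% power with 105 v 210 and 90% with 130 v 130.

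Part 1 of the same section (equivalence of DVD and face-to-face) uses a "common standard deviation for AQLQ of 0.77". It derives this openly as 25% below 1.03, gives a reason, and adds a fallback at an SD of 0.89. The summary then plans to analyse 210, 210 and 105 patients.

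**The concern.** A two-group t-test of mean AQLQ needs the spread of the outcome between patients within an arm. The protocol introduces 0.41 only as the SD that accompanies a threshold for change within a person, and nowhere says that it is also the between-patient spread. A second scenario may reasonably vary the difference to be detected. Here the SD changes as well, by a factor of 1.03 / 0.41 = 2.5, although the outcome, population and comparisons stay the same. How much patients vary does not depend on which difference one hopes to find.

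What is at stake is a stated power and two stated sample sizes in the justification for superiority. A reader could take from them that superiority on AQLQ can be settled with 26 or 30 patients. The trial's own size does not rest on them.

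**Working it through.** **Inputs, all from Protocol section 8.1.** Difference d = 0.5; one-sided α = 0.05; stated power 90%; stated sizes 10 v 20 and 13 v 13; SD 0.41. The other SDs the protocol gives for AQLQ are 1.03 (second superiority calculation), 0.77 (equivalence) and 0.89 (equivalence fallback). Planned analysed arms are 210, 210 and 105.

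**Formula.** For a two-sample t-test with common SD σ, the non-centrality is δ = d / (σ √(1/n₁ + 1/n₂)) on n₁ + n₂ − 2 degrees of freedom. Power is the probability that a non-central t variable with that δ exceeds the one-sided 5% critical value.

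**Step 1: reproduce the protocol's figures (σ = 0.41).**
- 10 v 20: √(1/10 + 1/20) = 0.3873; δ = 0.5 / (0.41 × 0.3873) = 3.15; 28 df, critical value 1.701; power 92.3%.
- 13 v 13: √(2/13) = 0.3922; δ = 0.5 / (0.41 × 0.3922) = 3.11; 24 df, critical value 1.711; power 91.5%.

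One step smaller, 9 v 18 gives 89.6% and 12 v 12 gives 89.4%. The stated sizes are therefore the smallest that reach 90%, and they follow correctly from the stated inputs.

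**Step 2: same sizes, with the protocol's other SDs.**

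| SD | Power, 10 v 20 | Power, 13 v 13 | Needed for 90%, 1:2 | Needed for 90%, 1:1 |
|---|---|---|---|---|
| 0.41 | 92.3% | 91.5% | 10 v 20 | 13 v 13 |
| 0.77 | 49.6% | 48.6% | 31 v 62 | 42 v 42 |
| 0.89 | 40.9% | 40.0% | 42 v 84 | 55 v 55 |
| 1.03 | 33.7% | 32.9% | 55 v 110 | 74 v 74 |

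For example, 10 v 20 at SD 1.03 gives δ = 0.5 / (1.03 × 0.3873) = 1.25, below the critical value of 1.701. At SD 1.03 the sizes needed are 55/10 = 5.5 and 74/13 = 5.7 times those stated.

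**Step 3: check the second calculation.** With d = 0.38 and σ = 1.03, power is 92.4% for 105 v 210 and 90.7% for 130 v 130. This agrees with the protocol's 92% and 90%.

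**Step 4: planned arms, d = 0.5, σ = 1.03, test against zero.** Power is 99.2% for 105 v 210 and over 99.9% for 210 v 210.

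**Step 5: the same arms under the stated decision rule.** The analysis plan for superiority rejects superiority if the one-sided 95% interval includes +0.3. Replacing d by 0.5 − 0.3 = 0.2 gives, at σ = 1.03, δ = 1.63 for 105 v 210 (power 49%) and δ = 1.99 for 210 v 210 (power 63%). Under that rule 55 v 110 and 74 v 74 would each have about 32%. Figures from the t-test against zero therefore do not carry over to the +0.3 rule.

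**The case against.** **The claim is conditional and the sums are right.** The protocol says 90% power if the SD is 0.41, and given that SD it is correct. This stands: the fault is an unsupported input. A reader might infer a miscalculation, and step 1 shows there is none.

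**The documents do not show what 0.41 is.** The protocol does not say how it was derived, and the cited source is not available here. An SD of individual change scores would itself be a between-patient quantity, and section 3.1 frames outcomes as changes from baseline. This also stands as far as it goes, so it cannot be asserted that 0.41 is definitely some other quantity. What the text does show is an unexplained move from a within-person context to a between-patient SD, against 1.03 one paragraph later.

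**Nothing depends on it.** The planned 210/210/105 matches the equivalence calculation, and the second superiority calculation already demands far more than 13 per arm. This stands and limits the consequence. A reader might infer that the trial is too small for superiority because of this error. The documents do not support that: against zero, the planned arms keep over 99% power for 0.5 at SD 1.03.

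**Different SDs may be legitimate.** A reader might conclude that one SD must be used throughout section 8.1. That goes too far. The 0.77 has its own stated rationale, the comparison of two breathing interventions. Whether that rationale is sound is a separate question, and replacing 0.77 would reopen the equivalence sizing. The 0.41 has no comparable justification.

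**Conclusion.** The point holds as a minor error in the sample-size text. Under each of the other SDs in section 8.1 (0.77, 0.89 and 1.03), power for a 0.5 difference at one-sided 5% is about 33–50% with 10 v 20 or 13 v 13, where the protocol states 90%. The value most directly comparable is 1.03, used for the same two comparisons in the next paragraph; it gives 33.7% and 32.9%.

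This assumes a two-sample t-test against zero with equal SDs, as the protocol specifies. Because the derivation of 0.41 is not given, the result is shown over the range of the protocol's other SDs and not tied to one value.

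Two stronger conclusions are not supported. The recruitment target of 585 is not undermined, since it does not derive from these sizes. Nor may the over 99% for the planned arms be read as power for the trial's superiority decision. It is power against zero; under the +0.3 rule, with a true difference of 0.5 and SD 1.03, power is about 49% for face-to-face and 63% for DVD against usual care.

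**What to change.** In section 8.1, sample size part 2, do one of the following:

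1. Delete the calculation based on 0.5 and 0.41, and rely on the one based on 0.38 and 1.03, whose stated powers reproduce.
2. Keep the target of 0.5 but redo the calculation with SD 1.03. For 90% power at one-sided 5% it then needs 55 face-to-face v 110 usual care, and 74 per arm for DVD v usual care.

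In either case, label every power figure in this part as power for a test against zero, including any statement that the planned arms give over 99% for a 0.5 difference. Add that this is not the power under the +0.3 rule in the analysis plan for superiority.

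The cost is a text correction. It changes neither the recruitment target nor the equivalence calculation with SD 0.77.

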#### Summary:

We aim to analyse 210 in each of the DVD and usual care arms and 105 in the face-to-face breathing retraining arm). Assuming a 10% dropout rate, we will therefore aim to recruit a total sample size of 585 patients (234 in each of the DVD and 'usual care' arms and 117 in the 'face-to-face' physiotherapy arm).

#### Statistical Analysis:

#### 1. Analysis plan for equivalence study

Analysis and reporting of the equivalence comparison will follow published guidelines. It is known that full analysis set or ITT may lead to bias (from protocol violators, withdrawals and dropouts) and a resultant increase in type 1 error risk. Therefore, for the equivalence study, an ITT and a per protocol analysis will run simultaneously, neither having supremacy over the other. They should hopefully lead to similar conclusions giving the study a robust interpretation.

A 95% CI will be constructed for the mean difference in 12 month total AQLQ score between the DVD arm and the 'face-to-face' breathing retraining arm. Since the equivalence boundary is set at 0.3, equivalence will be declared if the 95% CI is wholly included between -0.3 and +0.3. If equality is not evident, then ANCOVA will be used to examine whether the 'face-to-face' breathing retraining arm is superior to the DVD arm via examination of the difference (and 95% confidence interval) of 12 month total AQLQ score (and each of the four domain scores) before and after adjustment for baseline AQLQ score and potential covariates such as age, gender, practice, smoking status etc.

BREATHE Page 27 of 35 Protocol v6 01-08-2014

ANCOVA will also be used to analyse the difference (and 95% confidence interval) for the secondary outcome measures (ACQ, lung function, fraction of exhaled nitric oxide, EuroQOL, anxiety and depression score, hyperventilation and patient enablement scores) at 12 months before and after adjustment for baseline values and potential confounders. Since we have data on AQLQ, ACQ and HADS at four time points (baseline, 3, 6 and 12 months) a repeated measures analysis will be used to examine change in each of these outcomes over time. For those secondary outcomes which involve count data (i.e. oral corticosteroid courses, bronchodilator use, asthma related healthcare resource use), Poisson regression analyses with a log link function will be performed to give rate ratios (and their 95% confidence intervals) in the DVD and 'face-to-face' breathing retraining arm both before and after adjustment for potential confounders such as smoking status and sociodemographic factors.

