#### 2. Analysis plan for superiority study

Baseline comparability between the three arms of the trial will be evaluated by examination of summary statistics (the mean and standard deviation or median and interquartile range for continuous variables, dependent on their distribution, and the number and percentage for categorical variables). In accordance with CONSORT guidelines, all comparative analysis will be conducted on an intention to treat (ITT) basis with a per protocol analysis performed as a sensitivity analysis.

For the primary outcome, analysis of covariance (ANCOVA) will be used to examine the 12-month total AQLQ score (and each of the four domain scores) across the three arms with initial adjustment for baseline AQLQ score and then for other potential covariates such as age, gender, practice, smoking status etc. Pair wise comparisons of AQLQ differences will be examined between the 'usual care' arm and each of the DVD and 'face-to-face' breathing retraining arms via calculation of one sided 95% confidence intervals. If the confidence interval includes +0.3 then superiority of either the DVD or 'face-to-face' breathing retraining arms over usual care will be rejected.

In a similar way, ANCOVA will also be used to analyse the continuous secondary outcome measures (ACQ, lung function, fraction of exhaled nitric oxide, EuroQOL, anxiety and depression score, hyperventilation and patient enablement scores). Since we have data on AQLQ, ACQ and HADS at four time points (baseline, 3, 6 and 12 months) a repeated measures analysis will be used to examine change in each of these outcomes over time. The 'usual care' arm will be compared to each of the DVD and 'face-to-face' breathing retraining arms in turn.

For those secondary outcomes which involve count data (i.e. oral corticosteroid courses, bronchodilator use, asthma related healthcare resource use), Poisson regression analyses with a log link function will be performed to give rate ratios in the DVD and 'face-to-face' breathing retraining arm compared to 'usual care' both before and after adjustment for potential confounders such as smoking status and sociodemographic factors.

BREATHE Page 28 of 35 Protocol v6 01-08-2014

Data and all appropriate documentation will be stored for a minimum of 5 years after the completion of the trial, including the follow-up period.

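### The equivalence verdict names no baseline adjustment and holds adjusted ANCOVA back until equivalence has failed, so a valid interval is wider than it need be

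*Protocol*

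**What the plan says.** Protocol section 8.1, Analysis plan for equivalence study, sets the deciding quantity for DVD against face-to-face: "A 95% CI will be constructed for the mean difference in 12 month total AQLQ score between the DVD arm". Equivalence requires the whole interval to lie within ±0.3, and ITT and per-protocol analyses carry equal weight. No covariate is mentioned at this step. The next step is conditional: "If equality is not evident, then ANCOVA will be used to examine whether the 'face-to-face' breathing retraining arm is superior to the DVD arm". Only there does baseline AQLQ enter for this pair of arms, with results given before and after adjustment.

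The Analysis plan for superiority study, in the same section, analyses the same 12-month score by ANCOVA across the three arms "with initial adjustment for baseline AQLQ score", with further covariates added afterwards.

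The equivalence sample size rests on a plain two-group t-test of equivalence, with 210 analysed on DVD and 105 on face-to-face. The protocol says that these numbers "are required to assess treatment equivalence with 90% power using an equivalence boundary for AQLQ of 0.3". It assumes "that the expected between group difference in mean AQLQ is zero" and a "common standard deviation for AQLQ of 0.77 and a lower/upper limit of -0.3/+0.3 for the 95% confidence interval". No baseline covariate or correlation enters that calculation. Section 4.1 has AQLQ completed at the baseline visit, before randomisation, so it is available in every arm.

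**The concern.** An equivalence conclusion depends on how narrow the interval is. The protocol has a prognostic baseline measure of the primary outcome in every participant and uses it from the start for superiority. For equivalence it brings the measure in only after the interval has failed to fit within the margin, and then for a different question, whether face-to-face is superior. The more precise estimate is therefore not the one that decides equivalence.

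Equivalence is one of the two aims for which section 3 describes the trial as powered. The comparison of DVD with face-to-face also determines whether cost minimisation is done (section 7, Health economic evaluation, where the condition is worded as non-inferiority). What is at stake is a higher chance of an inconclusive result when the two programmes truly perform alike.

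**Working it through.** **Inputs from the protocol (section 8.1).** Analysed numbers 210 (DVD) and 105 (face-to-face); margin 0.3; true difference 0; two-tailed 5%, hence a 95% CI; SD 0.77, with 0.89 as the protocol's fallback and 1.03 from its earlier breathing-exercise trial.

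**Assumption not in the protocol.** The correlation r between baseline and 12-month AQLQ is taken as 0.3, 0.5 or 0.7. Restricting entry to AQLQ below 5.5 may lower it, so the bottom of the range is plausible.

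**Step 1: the stated power.**
- SE = 0.77 × √(1/210 + 1/105) = 0.77 × 0.1195 = 0.092.
- One bound at 2.5%: Φ(0.3/0.092 − 1.96) = Φ(1.30) = 90.3%. With SD 0.89 the same formula gives 80.5%. Both stated powers (90% and 80%) reproduce, but only for a single bound.
- The declared rule needs both bounds: 2 × 0.903 − 1 = 80.6%, or 80.3% with the exact t calculation. This 80% is the starting point below. The gap from 90% is a separate sample-size issue.

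**Step 2: the effect of adjustment if the SD is that of raw 12-month scores.** ANCOVA on baseline replaces SD by SD × √(1 − r²). The multipliers are 0.954, 0.866 and 0.714 for r = 0.3, 0.5 and 0.7, so the interval narrows by about 5%, 13% and 29%. At SD 0.77 the 95% half-width is 1.96 × 0.092 = 0.180 unadjusted, and 0.172, 0.156 and 0.129 adjusted.

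Power for the 95% CI to lie within ±0.3 (exact t, one degree of freedom lost to the covariate):

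| SD | Unadjusted | r = 0.3 | r = 0.5 | r = 0.7 |
|---|---|---|---|---|
| 0.77 | 80% | 85% | 93% | 99% |
| 0.89 | 61% | 68% | 80% | 95% |
| 1.03 | 36% | 44% | 60% | 85% |

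At SD 0.77, a correlation of about 0.44 brings the declared rule to 90%.

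**Step 3: other meanings of 0.77.** The protocol does not say which SD this is.
- *Residual SD after adjustment.* The raw SD is 0.77/√(1 − r²) = 0.807, 0.889 or 1.078. Unadjusted power is 75%, 61% or 28%; adjusted power is about 80% throughout.
- *SD of change from baseline* (section 3.1 describes outcomes as changes). With equal SDs at both times, the raw SD is 0.77/√(2(1 − r)) = 0.651, 0.770 or 0.994. Unadjusted power is 94%, 80% or 42%; adjusted power is 96%, 93% or 88%.

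The size of the gain depends on which SD is meant. Its direction does not.

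**The case against.** The word unadjusted does not appear. The equivalence plan names no model, and the three-arm ANCOVA in the superiority plan could supply the DVD versus face-to-face contrast, although the contrasts it names are against usual care. The model behind an interval is often left to the SAP, which is not shown here. This stands as a caution about certainty. It does not remove the point, because the protocol sets an order of analyses in which adjustment for this pair follows failure, and the plain two-group sizing fits the unadjusted reading.

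It is also fair that validity is not at stake. In a randomised comparison the unadjusted interval is unbiased and keeps its error rate. The loss is one of efficiency.

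Two stronger readings are tempting, and the protocol does not support them:

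- **A reader might infer that equivalence is the least powered comparison.** That is so only if superiority is tested against zero. The superiority plan rejects superiority when the one-sided 95% interval includes +0.3. At a true difference of 0.38 and SD 1.03, power under that rule is Φ(0.08/0.123 − 1.645) ≈ 16% for face-to-face and Φ(0.08/0.1005 − 1.645) ≈ 20% for DVD, both below the 36% for equivalence at the same SD.
- **A reader might infer that a chance baseline imbalance passes in full into a raw 12-month comparison.** The SE of that imbalance is 0.12 SD, which would be 40% of the margin if the SD were 1. In fact it passes through only in proportion to the slope of 12-month on baseline score. With equal SDs and r from 0.3 to 0.7 that is about 12% to 28% of the margin at SD 1, or 9% to 21% at SD 0.77. The unadjusted SE already contains this variation, so it is not a harm additional to interval width.

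**Conclusion.** The point holds as one of efficiency. On its natural reading the protocol decides equivalence with a less precise estimate than the one it uses for superiority on the same outcome, and keeps the better one for after equivalence has failed. If 0.77 is a raw-score SD, power under the declared rule is about 80% unadjusted, against 85% to 99% adjusted for r from 0.3 to 0.7. If 0.77 is a residual SD, the unadjusted analysis falls to between 75% and 28% against about 80% adjusted. These figures rest on an assumed correlation, a true difference of zero and full analysed numbers of 210 and 105. Were the correlation near zero, adjustment would cost one degree of freedom. The documents do not support calling the unadjusted interval biased or invalid. The change should be made, but the trial does not fail without it.

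**What to change.** Amend the equivalence plan to state, before unblinding, that the decision in both the ITT and per-protocol sets uses the 95% CI for the DVD minus face-to-face difference from an ANCOVA of 12-month total AQLQ adjusted for baseline AQLQ. Report the unadjusted difference as a sensitivity analysis. If the SAP already specifies an adjusted interval, bring the protocol text into line with it. Timing matters because choosing between the two intervals after seeing the results would be data-driven. It would also help to say whether 0.77 is the SD of raw scores, of changes or of residuals, so that power can be restated on the same basis as the analysis. The cost is a sentence or two of text, with no new data and no extra participants.

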The methodology of this RCT is based on that of the GLAD study, a 2 armed RCT comparing face-to-face physiotherapist breathing instruction with a control of asthma education (16).

We will perform a pragmatic observer blinded 3 arm parallel group randomised controlled trial comparing a breathing retraining programme delivered through a DVD with a 'face-to-face' physiotherapist programme and a 'control' arm receiving usual care for adults with asthma and impaired health status. Three arms are needed to confirm superiority of the DVD over usual care and comparable efficacy to 'face-to-face' physiotherapy. The study is dual powered to show superiority of the breathing retraining DVD over usual care and equivalence with 'face-to-face' physiotherapist instruction. The focus of this research is on the DVD, as this is most likely to be translated into every-day practice. As the face-to-face physiotherapy already has evidence of effectiveness, and our aim is to show comparable effectiveness of the DVD and superiority of the DVD over usual care, we are using a 2:2:1 randomisation plan (DVD: usual care: face-to-face physiotherapy). This will reduce the costs and logistics of the trial, as the face-to-face intervention is associated with the largest use of time and resources. Subjects will be recruited in the setting of UK general practices who are members of the South-West Primary Care Research Network. Broad entry criteria will be used to allow representative patients to participate and so provide the trial with external validity. The RCT is described in detail below. An internal pilot will initially occur in two GP practices. An assessment of the recruitment rate and of the logistics of the trial protocol will

BREATHE Page 16 of 35 Protocol v6 01-08-2014

be made after this internal pilot, and minor protocol adjustments made as appropriate. Provided significant protocol changes are not made, it is planned to include the data from subjects participating in the pilot in the final analysis.

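### The equivalence declaration and the cost-minimisation trigger rest on the DVD versus face-to-face difference alone, so two ineffective programmes would pass as often (about 80%) as two equally effective ones

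*Protocol*

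**What the plan says.** Section 8.1, Statistical Analysis, part 1 (equivalence) sets the contrast, which involves the two active arms only: "A 95% CI will be constructed for the mean difference in 12 month total AQLQ score between the DVD arm and the 'face-to-face' breathing retraining". The decision follows from it: "equivalence will be declared if the 95% CI is wholly included between -0.3 and +0.3". ITT and per-protocol analyses run side by side with equal standing. No further condition is attached.

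Part 2 of the same section (superiority) separately compares each active arm with usual care on 12-month AQLQ by one-sided 95% confidence intervals, and rejects superiority if the interval includes +0.3. Nothing orders the two analyses or makes one depend on the other.

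Section 3, Phase 2 gives the reason for the design: "Three arms are needed to confirm superiority of the DVD over usual care and comparable efficacy", the latter being judged against face-to-face training. Section 1.1 describes the aim as including equivalence to a treatment already known to help. Section 8.1, Sample Size, part 1 takes the 0.3 boundary from an earlier asthma equivalence study and adds the criterion that a margin "should be smaller than differences observed in superiority trials of the active comparator".

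Section 7, Health economic evaluation, starts cost minimisation once the DVD is shown non-inferior to face-to-face, without asking whether either beat usual care.

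**The concern.** The conclusion wanted is that the DVD gives a benefit comparable to that of an effective programme. A narrow interval between DVD and face-to-face shows only that the two arms ended up alike. They may be alike because both work, or because neither did in this population at 12 months, for example through poor adherence. The rule cannot tell these apart.

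The usual-care arm can, but the rule does not consult it. At stake are the wording of a pre-specified declaration and the choice of economic analysis. If equivalence is declared when neither arm beats usual care, the word invites a reading of comparable benefit that the data do not support, and the economic section then compares the two programmes on cost alone. Leaving the link open also lets the interpretation be chosen once the results are known.

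**Working it through.** **Inputs** (all from Section 8.1)
- Analysed: 210 DVD, 210 usual care, 105 face-to-face.
- Margin ±0.3; planned difference: "that the expected between group difference in mean AQLQ is zero".
- Level and SD: "a two tailed 5% significance level; common standard deviation for AQLQ of 0.77".
- Fallback for 80% power: "as long as the between group SD was no higher than 0.89".
- Effect from the earlier breathing-training trial: 0.38 (SD 1.03) at 6 months.

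**Step 1: reproduce the stated power.** The protocol says these numbers "are required to assess treatment equivalence with 90% power using an equivalence boundary for AQLQ of 0.3".
- SE = 0.77 × √(1/210 + 1/105) = 0.0920.
- One bound at 2.5%: Φ(0.3/0.0920 − 1.96) = Φ(1.30) = 0.903.
- At SD 0.89 the same formula gives 0.805.

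Both stated figures (90% and 80%) are reproduced as the power for one bound.

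**Step 2: probability of the declaration as written.** Both limits of the 95% CI must lie inside the margin. When the true difference is zero, P = 2 × Φ(0.3/SE − 1.96) − 1.
- SD 0.77: 2 × 0.903 − 1 = 0.806 (0.803 with the non-central t).
- SD 0.89: 0.610.
- SD 1.03: 0.367.

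So about 0.80, not 0.90, is the relevant figure at the protocol's SD.

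**Step 3: dependence on effectiveness.** The formula contains the SD, the sample sizes and the mutual difference, but not the effect over usual care. A three-arm normal simulation (2,000,000 replicates, SD 0.77) confirms this: 0.807 with both effects 0, 0.807 with both 0.38, 0.806 with both 0.5.

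**Step 4: add a condition on usual care.** The same simulation gives the probability that equivalence is declared and the condition is met:

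| SD 0.77 | Both effects 0 | Both effects 0.38 |
|---|---|---|
| Rule as written | 0.807 | 0.807 |
| Face-to-face bound above 0 | 0.023 | 0.805 |
| DVD bound above 0 | 0.034 | 0.807 |
| Both bounds above 0 | 0.009 | 0.805 |
| Face-to-face bound above +0.3 | 0.000 | 0.152 |
| DVD bound above +0.3 | 0.000 | 0.219 |
| Both bounds above +0.3 | 0.000 | 0.098 |

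The bounds are lower one-sided 95% limits of the difference from usual care. At SD 1.03 and effect 0.38, the rule as written gives 0.367, and 0.356 with either the face-to-face condition or both conditions at 0. With t quantiles these are about 0.36 and 0.35. With the +0.3 conditions it is 0.036 (face-to-face) or 0.034 (both).

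**Step 5: why the threshold matters.** Face-to-face against usual care also has SE 0.0920.
- A lower bound above 0 needs an observed difference above 1.645 × 0.0920 = 0.151. At a true effect of 0.38 this is nearly certain: Φ((0.38 − 0.151)/0.0920) = Φ(2.49) = 0.99.
- A lower bound above +0.3 needs 0.451, which exceeds the planned effect: Φ((0.38 − 0.451)/0.0920) = Φ(−0.77) = 0.22, before equivalence is also required.

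**The case against.** The best defence is that the plan as a whole does use usual care. The synopsis hypothesis is joint: better than usual care and similar to face-to-face. Section 3 calls the study dual powered, and Section 8.1 tests both active arms against usual care on the same endpoint. With two null programmes, the chance that equivalence is declared and either arm also passes the protocol's +0.3 rule is essentially nil. The economic section also costs both programmes against usual care, so an ineffective DVD would look poor there; cost minimisation does not replace that comparison. All of this stands, and it limits the harm. A linking sentence might also sit in an analysis plan that is not available. However, the protocol itself fixes the declaration and the trigger, and does so without the condition.

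Three stronger inferences are tempting and not supported:
- A reader might infer that the plan would lead to roll-out of an ineffective DVD. That would require ignoring the pre-specified usual-care comparison.
- A reader might call the 80% a false-positive rate. Two programmes with equal effects are equivalent, so the declaration is true; it misleads only when read as comparable benefit.
- A reader might conclude that the 0.3 margin is invalid. On the protocol's own figures the margin meets the criterion it cites, since 0.38 exceeds 0.3, and it was also taken from a previous asthma trial. The margin is 79% of that estimate (0.3/0.38), which was measured at 6 months rather than 12. That is a reason to check the effect in this trial, not proof that the margin fails.

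**Conclusion.** The point holds as a gap in the link between two planned analyses; no comparison is missing. At SD 0.77 the declaration occurs with probability about 0.80 for two null programmes and for two equally effective ones. By itself it therefore cannot support the aim of matching a programme of known benefit, and neither can an economic step triggered by it alone.

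The figures assume approximately normal estimates, the planned 210/210/105 analysed, one analysis set, equal true effects of the two programmes, and the same SD whether or not they work. A larger SD lowers the level (0.61 at 0.89, 0.37 at 1.03) but not the equality between the scenarios. The remedy is cheap only if beating usual care is defined as a lower bound above 0. The change should be made, but it concerns interpretation and does not invalidate the design.

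**What to change.** Add to Section 8.1, equivalence analysis, a statement to this effect:

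> Equivalence of DVD and face-to-face will be interpreted as comparable benefit only if the face-to-face arm (and, for the headline claim, the DVD arm) is better than usual care on 12-month total AQLQ. For this purpose, better means that the lower one-sided 95% confidence bound of the difference lies above 0; the +0.3 threshold of the superiority analysis does not apply here. Otherwise the DVD versus face-to-face interval will be reported as uninformative about effectiveness.

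Make the cost-minimisation step in Section 7 subject to the same condition.

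This needs no new data or patients, and the superiority analysis already calculates the one-sided bounds. The price is that the equivalence claim becomes conditional. At an effect of 0.38 its probability hardly moves (about 0.80 at SD 0.77; about 0.36 to 0.35 at SD 1.03), while under zero effect it falls from about 0.80 to about 0.02 (face-to-face condition) or 0.01 (both) at SD 0.77. The threshold must be written out. If the condition were taken to mean the +0.3 rule, the claim would have only a 0.10–0.15 chance at the planned effect (both conditions, or face-to-face alone).
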